1.2.5.2 Injection Site Reactions

In a repeat-dose GLP toxicology study in Cynomolgus monkeys, BOS161721 was administered every 2 weeks by IV or SC for 3 months (a total of 7 doses). There were no injection site reactions in animals dosed subcutaneously. Further, there were no reports of injection site reactions in the 26-week GLP toxicology study in Cynomolgus monkeys.

Based on the phase 1 SAD study (BOS161721-01), incidence of injection site reactions in subjects who received BOS161721 was similar to placebo.

Patients will be monitored for local injection site reactions in this study (see [Section 6.2.7](#)).

1.2.5.3 Immune Complex Disease

The potential risk of immune complex disease for BOS161721 is theoretical, based on the known risks associated with mAbs. The administration of a mAb can result in the formation of ADAs. Administration of the mAb in the presence of ADA may result in the formation of circulating antibody-antigen complexes potentially resulting in altered BOS161721 levels or activity or deposition of the complexes in microvasculature. Complement is frequently involved in the latter setting, and the breakdown products of complement attract polymorphonuclear leukocytes to the site of deposition where they can provoke local tissue damage through specific or nonspecific release of enzymes. Two of the more common end-organ targets are the blood vessels (vasculitis) and kidney (nephritis). These clinical manifestations represent immune complex disease or Type III hypersensitivity. Although BOS161721 is a humanized mAb, ADAs may develop; however, the likelihood of occurrence of immune complex disease with BOS161721 is low. The findings of immune complex disease are typically reversible when mAb administration stops and the antibody-antigen complexes are cleared from the body.

Based on the phase 1 SAD study (BOS161721-01), immune complex disease in subjects who received BOS161721 was not observed.

1.2.5.4 Infections

BOS161721 is expected to diminish the activity of T-cell, B-cell and NK-cell lines. Like other medications modulating immune response, BOS161721 may increase the potential risk for infection, including serious infections. IL-21 produced by CD4+ T-cells is required to sustain the anti-viral function of CD8+ T-cells against chronic viral infections. Nonclinical evidence suggests that the risk of chronic viral infection recurrence or increased severity may occur with IL-21 inhibition.³⁵

These conditions will be fully characterized with clinical descriptions and routine laboratory and/or specialty testing and treated where indicated with appropriate local standard of care.

Patients with a history of opportunistic infection, including recurrent or severe disseminated herpes zoster or disseminated herpes simplex within the last 3 years, or any other underlying pathology predisposing to serious infection, are excluded from studies with BOS161721 (for further details please refer to the current IB for BOS161721).

Patients will be assessed for hepatitis B, and C, and HIV-1/2 combination, at screening.

Cryptosporidium Infection

Cryptosporidium infection was noted in patients with an IL-21 receptor loss-of-function gene mutation and similar findings of cryptosporidium infection have been observed in immunosuppressed liver transplant and human immunodeficiency virus patients.^{36,37} Since BOS161721 is expected to diminish the immunosurveillance activity of T-cell, B-cell, and NK-cell lines, a similar risk is biologically plausible with prolonged exposure to BOS161721.

Since the risk of opportunistic cryptosporidium infection increases with low levels of CD4+ T-cells,³⁷ patients with a CD4+ count < 500 cell/mm³ were excluded from the phase 1 SAD study (BOS161721-01). Patients with CD4+ count < 350 cells/mm³ and CD4+ count < 150 cells/mm³ will be excluded from the MAD and POC parts of the study, respectively. Patients exposed to investigational product who develop diarrhea during the course of the study should immediately undergo an assessment for opportunistic infection including stool for ova and parasites and stool examination for cryptosporidium. Positive cryptosporidium in stool sample at screening is an exclusion. Treatment by the Investigator where indicated should be guided by findings and be consistent with local standard of care.

Based on the phase 1 SAD study (BOS161721-01), infections in subjects who received BOS161721 was not observed.

1.2.5.5 Malignancy

The stimulatory effect of IL-21 on NK cells and CD8+ T-cells suggests the cytokine may have anti-tumor activity. Nonclinical studies have demonstrated significant anti-tumor effects of IL-21 in a number of tumor models. IL-21 therapy of human metastatic melanoma and renal cell carcinoma has demonstrated POC with significant increases in levels of perforin, granzyme B, and interferon gamma (IFN γ) expression in CD8+ T-cells and NK T-cells. Clinical response has been limited in these generally unmanageable diseases.

The impact of treatment with anti-IL-21 therapy on the development or growth of malignancies is not known; however, as with other immunomodulatory biologic agents, treatment with BOS161721 may result in an increase in the risk of malignancies. NK cell suppression by IL-21 neutralization may represent a biological mechanism for a potential risk for malignancy. Patients with a history or current diagnosis of cancer within the past 5 years, with the exception of non-melanoma skin cancer or cervical cancer in situ treated with apparent success with curative therapy, are excluded from the study.

Based on the phase 1 SAD study (BOS161721-01), malignancy in subjects who received BOS161721 was not observed.

1.2.5.6 Hepatic Function Abnormality

There is no substantial evidence suggesting BOS161721 is associated with liver function abnormality. However, as a precaution, patients with a history of abnormal

alanine aminotransferase (ALT) and/or aspartate aminotransferase (AST), or bilirubin at screening (ALT/AST > 2 × upper limit of normal [ULN]; total bilirubin > 1.5 × [ULN] and judged by the Investigator to be clinically significant) were excluded from the phase 1 SAD study (BOS161721-01), and will be excluded from this trial. Patients with a positive hepatitis B or C test or a history of alcohol dependence will also be excluded.

Based on the phase 1 SAD study (BOS161721-01), hepatic function abnormality in subjects who received BOS161721 was not observed.

1.2.5.7 Failure of Vaccination

IL-21 is a key cytokine in development of B-cells into immunoglobulin-secreting plasma cells. Abnormal signaling through the IL-21R/Janus Kinase (JAK)3/signal transducer and activator of transcription (STAT3) pathway leads to defective humoral immune responses to both T-dependent and T-independent antigens and impairs the establishment of long-lasting B-cell memory. Abnormal signaling through the pathway has been related to decreased specific antibody responses following vaccination, and to increased susceptibility to encapsulated bacterial infections.³⁸

The effect of BOS161721 was evaluated in in vivo single dose studies in Cynomolgus monkey in which the animals received vaccination to T-cell dependent KLH antigen to stimulate a TDAR. These in vivo studies demonstrated that BOS161721 significantly inhibited B-cell proliferation and IgG antibody responses to the KLH protein antigen in a dose-dependent fashion; however, BOS161721 administration did not affect anti-tetanus toxoid antibody data for IgM, IgG, IgG1, or immunoglobulin E (IgE) during the dosing phase in the same study.

1.2.5.8 Potential for Drug-Drug Interactions

Drug-drug interactions were not evaluated in the phase 1 SAD study (BOS161721-01), which included only healthy adult subjects. Use of prescription medications (with the exceptions of oral contraceptives), and over-the-counter (OTC) treatments including herbal supplements such as St John's Wort (except multivitamins), in the 2 weeks prior to screening was prohibited in the SAD study.

See [Section 4.5](#) for other specific exclusion criteria which support lowered risk of interactions, and [Section 4.6.1](#) for corticosteroid (CS) dosing. In addition, [Section 1.2.5.6](#) describes considerations for hepatic function for this study.

1.2.5.9 Potential Risk to Fetal Development

No data on preclinical reproductive toxicity are available at the time of this study.

2 STUDY OBJECTIVES AND ENDPOINTS

This trial has separate objectives and endpoints for the MAD phase 1b and POC phase 2 portions of the study. The primary, secondary, and exploratory objectives for each phase, as applicable, are described below with their corresponding endpoints.

2.1 Phase 1b Multiple Ascending Dose

OBJECTIVES	ENDPOINTS
Primary	

 To assess safety, tolerability, and immunogenicity of repeat doses of BOS161721 (20, 60, and 120 mg) administered SC in adult patients with moderately to severely active SLE on limited background standard of care treatment, in order to estimate the optimal dose 	
Safety Endpoints
 
 Incidence and severity of AEs and SAEs, related AEs, AEs leading to study drug discontinuation, AEs by severity and relatedness Injection site reactions Columbia Suicide Severity Rating Scale (C-SSRS) 12-lead ECGs parameter results at each visit and change from baseline Vital signs (blood pressure [BP], heart rate, and temperature) parameter results at each visit and change from baseline Clinical laboratory results and change from baseline Physical examinations changes from baseline ADAs Study drug exposure/compliance
Secondary	

 To characterize the PK of BOS161721 and select the optimal dose of BOS161721 based on safety, PK, and PD effects in patients with moderately to severely active SLE 	
Pharmacokinetic Endpoints
 
 BOS161721 concentration by visit and time point Maximum observed concentration (C_{max}), T_{max}, area under the concentration-time curve (AUC), terminal elimination half-life ($t_{1/2}$), systematic clearance (CL), volume of distribution (V_d) 
Pharmacodynamic Endpoints
 
 Results and changes (or shifts) from baseline to each visit in phosphorylated signal transducer and activator of transcription 3 (pSTAT3), C3 and C4 levels, and leukocyte immunophenotype Results and changes (or shifts) from baseline in anti-double-stranded DNA (dsDNA), antinuclear antibodies (ANA), anti-Sjögren syndrome A and B (SSA, SSB), Smith (Sm), and antiphospholipid (APL) autoantibodies at each visit Results and changes (or shifts) from baseline in abrogation of IL-21 gene signature at each indicated visit
Exploratory	

 CCI [REDACTED] 	
 CCI [REDACTED]

	
 - CCI [REDACTED] [REDACTED] [REDACTED] [REDACTED] • CCI [REDACTED] [REDACTED] [REDACTED] [REDACTED] [REDACTED] [REDACTED] [REDACTED] [REDACTED] [REDACTED] • CCI [REDACTED] [REDACTED] [REDACTED] [REDACTED] [REDACTED]

 • CCI [REDACTED] [REDACTED] [REDACTED] [REDACTED] [REDACTED] 	
 • CCI [REDACTED] [REDACTED] [REDACTED] [REDACTED]

 • CCI [REDACTED] [REDACTED] [REDACTED] [REDACTED] 	
 • CCI [REDACTED] [REDACTED]

2.2 Phase 2 Proof of Concept

OBJECTIVES	ENDPOINTS
Primary	

 • To demonstrate a superior effect of BOS161721 at the chosen dose compared with placebo for response on the SRI-4 	Primary Efficacy Endpoint 
 • The proportion of patients with a SRI-4 response at Day 210 (see Section 6.3.4.1)
Secondary	

 • To demonstrate a superior effect of BOS161721 at the chosen dose compared with placebo for response on clinical indicators of SLE activity, in adult patients with moderately to severely active SLE on limited background standard of care treatment 	Secondary Efficacy Endpoints 
 • The proportion of patients with: 
 - SRI-4 response at each visit - SRI-5 and SRI-6 response at each visit (Section 6.3.4.2) - a sustained reduction from baseline of oral corticosteroid (CS) (≤ 7.5 mg/day and $<$ Day 0 dose) between Day 150 and Day 210 - new or recurrent BILAG flares (≥ 1 qualifying BILAG A or > 1 qualifying BILAG B) through Day 210 - PGA worsening - a BICLA response - a CLASI response

	
 - medication failures • The changes and percent changes from baseline in: 
 - CLASI - PGA - Total number of swollen joints, tender joints, and active joints (swelling and tenderness in the same joint) in the ACR-28 joint count - SLEDAI-2K - SLICC/ACR damage index • Time to medication failure • Group mean percent reduction in CS administration from baseline Day 0 dose through Day 210 in patients receiving ≥ 7.5 mg/day prednisone equivalent at Day 0 • Duration of longest SRI-4 response • Time to first BILAG flare (≥ 1 new or recurrent BILAG A or > 1 new or recurrent BILAG B) relative to baseline through Day 210
--	--

Safety


 • To assess safety and tolerability of repeat doses of BOS161721 at the chosen dose administered SC in adult patients with moderately to severely active SLE on limited background standard of care treatment 	
Safety Endpoints
 
 • Incidence and severity of adverse events (AEs) and serious adverse events (SAEs), related AEs, AEs leading to study drug discontinuation, AEs by severity and relatedness • Injection site reactions • C-SSRS • 12-lead ECGs parameter results at each visit and change from baseline • Vital signs (blood pressure [BP], heart rate, and temperature) parameter results at each visit and change from baseline • Clinical laboratory results and change from baseline • Physical examinations changes from baseline • ADAs • Study drug exposure/compliance
---	---

Exploratory

 • CCI [REDACTED] 	
 • CCI [REDACTED] • [REDACTED] • [REDACTED] • [REDACTED] • [REDACTED] • [REDACTED] • [REDACTED]

 • CCI [REDACTED] 	
 • CCI [REDACTED] • [REDACTED] • [REDACTED] • [REDACTED] • [REDACTED]

	
• CCI [REDACTED]

• CCI [REDACTED]	
• CCI [REDACTED]

• CCI [REDACTED]	
• CCI [REDACTED]

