	
All safety analyses will be performed using the safety analysis set (SS), defined as all patients who receive at least 1 dose of study treatment. All efficacy analyses will be performed using the full analysis set (FAS), defined as all patients who receive at least 1 dose of study treatment and have at least 1 evaluable post-baseline efficacy evaluation. Select efficacy analyses may also be performed on the per protocol (PP) set.
 
Binary efficacy endpoints, including the primary efficacy endpoint, will be assessed via Pearson's chi-squared analysis.
 
Continuous efficacy endpoints will be assessed via analysis of variance (ANOVA) or analysis of covariance (ANCOVA) when applicable, adjusting for the baseline value. Repeated measures mixed models may be performed to evaluate data collected at each visit and overall. Time-to-event endpoints will be assessed via Kaplan-Meier methodology and treatment will be compared using the log-rank test.
 
Adverse event data will be coded to system organ class and preferred term using the Medical Dictionary for Regulatory Activities (MedDRA). The number and percentage of patients experiencing any treatment-emergent AE, overall, and by system organ class and preferred term will be tabulated. Treatment-emergent AEs will also be summarized by severity and relationship.
 
Concomitant medications will be summarized, based on coded terms, using frequency and percentage of patients. Observed values and changes from baseline in vital signs, ECG readings, and hematology and clinical chemistry parameters, will be summarized at each individual visit.

--	---

TABLE OF CONTENTS

A RANDOMIZED DOUBLE-BLIND PHASE 1B/2 COMBINED STAGGERED MULTIPLE DOSE ESCALATION STUDY OF BOS161721 IN SYSTEMIC LUPUS ERYTHEMATOSUS (SLE) PATIENTS ON A BACKGROUND OF LIMITED STANDARD OF CARE	1
CLINICAL PROTOCOL APPROVAL FORM	2
CONFIDENTIALITY AND INVESTIGATOR STATEMENT	4
PROTOCOL SUMMARY	5
TABLE OF CONTENTS	20
LIST OF IN-TEXT TABLES	23
LIST OF IN-TEXT FIGURES	24
LIST OF ABBREVIATIONS	25
1 INTRODUCTION AND RATIONALE	29
1.1 Indication	29
1.2 Background and Rationale	29
1.2.1 Overview of the Disease State	29
1.2.2 BOS161721 Development	29
1.2.2.1 Interleukin-21	30
1.2.2.2 Preclinical Studies	31
1.2.2.3 Clinical Studies	33
1.2.3 Study Dose Selection	33
1.2.4 Risk-Benefit Assessment	35
1.2.5 Potential Risks	35
1.2.5.1 Anaphylaxis and Serious Allergic Reactions	36
1.2.5.2 Injection Site Reactions	36
1.2.5.3 Immune Complex Disease	37

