6.3.5 CLASI Response

The CLASI is a comprehensive tool for assessment of disease activity and damage in cutaneous lupus, shown to be valid, reliable, and sensitive to changes in disease activity.⁴⁸ Response is defined as 50% improvement from baseline in "A" or "B" scores. This assessment will be applied to all patients who have cutaneous disease activity.

For the secondary efficacy endpoint of CLASI response at Day 210, patient scores on MAD and POC studies will be compared with baseline for 50% improvement.

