6.4 Other Variables

6.4.1 SLICC/ACR Damage Index

The SLICC/ACR damage index is a validated instrument to assess damage, defined as irreversible impairment, continuously persistent for 6 months (ascertained by clinical assessment), occurring since the onset of lupus, and it is based on a weighted scoring system. This index records damage occurring in patients with SLE regardless of cause,

with demonstrated content, face, criterion, and discriminant validity.⁴⁹ It will be performed on Days 0 and 180.

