8.2.4 Secondary Efficacy Endpoint(s)

Binary efficacy endpoints will be assessed via Pearson's chi-squared analysis. Continuous efficacy endpoints will be assessed via analysis of variance (ANOVA) or analysis of covariance (ANCOVA) and treatment will be compared using the F-test. Repeated measures mixed models may be performed to evaluate data collected at each visit and overall. Time-to-event endpoints will be assessed via Kaplan-Meier methodology and treatment will be compared using the log-rank test. The secondary efficacy endpoints will be analyzed on the FAS and if needed repeated in the PP analysis set. Details including handling of missing data and "medication failures" will be available in the SAP.

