	
laboratory specimens (Table 2: Hematology, Chemistry, and Urinalysis) sent to their local laboratory for analysis and review by the study physician.
 
 Investigational Product Dosing: In cases when dosing cannot be performed during the protocol-designated windows, the Investigator should discuss each case with the Sponsor to determine whether it is a missed visit or whether the dosing can be performed outside protocol windows (as a protocol deviation). A minimum of 2 weeks must be maintained between consecutive doses. Patients who miss more than 2 doses of the study drug (whether consecutive or not) will be discontinued from the study and will undergo assessments as outlined in Section 5.5 (Premature Discontinuation). 	
ASSESSMENTS, Section 6.2.3, Vital Signs	
Replace:
 
Vital signs will be assessed on Day 0 at predose and at Day 0, 1 and 2 hours postdose, as well as on each of the scheduled visit days during the study (excluding PK-only site visits).
 
With:
 
Vital signs will be assessed on Day 0 at predose and at Day 0, 1 and 2 hours (\pm 15 minutes) postdose, as well as on each of the scheduled visit days during the study (excluding PK-only site visits).
	Flexible language is introduced for the timing of the vital signs.
ASSESSMENTS, Section 6.3.5, CLASI Response, Paragraph 1.	
Replace:
 
This assessment will be applied to all patients as all are required to have cutaneous disease activity.
 
With:
 
This assessment will be applied to all patients who have cutaneous disease activity.
	Inclusion criteria could be met without presence of mucocutaneous disease.

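### Sustained steroid reduction is tested in patients who cannot achieve it, and a damage index read on Days 0 and 180 can hardly register damage arising on treatment

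*Protocol*

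**What the plan says.** Section 2.2 (Phase 2 Proof of Concept) lists the proportion of patients with "a sustained reduction from baseline of oral corticosteroid (CS"). Success means at most 7.5 mg/day and less than the Day 0 dose between Day 150 and Day 210. The entry carries no restriction to patients who take a steroid. The companion endpoint in the same list, the group mean percent reduction in corticosteroid, is restricted to patients on at least 7.5 mg/day prednisone equivalent at Day 0.

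The same section lists "The changes and percent changes from baseline in" CLASI, PGA, three ACR-28 joint counts, SLEDAI-2K and the SLICC/ACR damage index.

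Section 6.4.1 defines damage as irreversible impairment that is "continuously persistent for 6 months (ascertained by clinical assessment"), and says of the index: "It will be performed on Days 0 and 180". Table 1 agrees and gives the Day 180 visit a window of 3 days either way.

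On the analysis set, Section 8.2.4 states: "The secondary efficacy endpoints will be analyzed on the FAS and if needed repeated in the PP analysis set". Section 8.2.1 defines the FAS by one dose and one evaluable post-baseline efficacy evaluation, with no condition on baseline steroid use. Section 8.2.3 applies the primary endpoint's superiority hypothesis, two-sided p below 0.10, to the secondary endpoints. Under inclusion criterion 8 (Section 4.4) a patient needs only one of the listed background options, so a steroid-sparing agent alone qualifies.

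**The concern.** For the steroid endpoint, the eligibility rule and the success rule do not fit together. A dose of 0 mg cannot fall below 0 mg, so some patients in the denominator have their outcome settled before randomisation. They pull both arms' rates towards zero and shrink the difference. The sponsor limited one of the two steroid endpoints to relevant patients and left the other open.

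For the damage index, the persistence rule is about as long as the interval between the two readings. An endpoint tested for superiority should be able to reflect what happens after treatment starts, and this one mostly cannot. At stake are a weakened steroid-sparing comparison and a damage result that could be misread as evidence that the drug does not affect damage.

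**Working it through.** **Plan's own figure.** Section 8.1 gives 96 evaluable patients for 62% vs 33%, two-sided alpha 0.10, 80% power and 2:1 allocation. The two-proportion formula with continuity correction gives 32 placebo + 64 active = 96, an exact match. Without the correction it gives 27 + 54 = 81, and uncorrected power at 32/64 is 86.2%. The figure concerns SRI-4 only and is not affected by this point.

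**Steroid endpoint.** Let q be the share of the FAS on 0 mg at Day 0, and let p1 and p0 be the true success rates among steroid users on active and placebo. In the FAS the rates are (1−q)p1 and (1−q)p0, so the difference is (1−q)(p1−p0), and no arm's rate can exceed 1−q.

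The protocol gives neither q nor the rates. Assumed here: p1 = 40%, p0 = 20%, q = 20% or 40%, with 96 patients and alpha 0.10.

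Power = Φ[(d − 1.645·SE0)/SE1], where d is the difference, SE0 = √[p̄(1−p̄)(1/n0+1/n1)], SE1 = √[p0(1−p0)/n0 + p1(1−p1)/n1], and p̄ is the pooled rate.

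| q | Analysis | n active:placebo | Rates | d | SE0 | SE1 | Power |
|---|---|---|---|---|---|---|---|
| 20% | whole FAS | 64:32 | 32% vs 16% | 0.16 | 0.0957 | 0.0872 | 0.512 |
| 20% | steroid users | 51:26 | 40% vs 20% | 0.20 | 0.1135 | 0.1042 | 0.551 |
| 40% | whole FAS | 64:32 | 24% vs 12% | 0.12 | 0.0866 | 0.0784 | 0.387 |
| 40% | steroid users | 38:19 | 40% vs 20% | 0.20 | 0.1325 | 0.1214 | 0.441 |

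First row as an example: (0.16 − 1.645 × 0.0957)/0.0872 = 0.03, and Φ(0.03) = 0.51. The gaps are 0.551 − 0.512 = 0.039 and 0.441 − 0.387 = 0.054, or about 4-5 points. Steroid users alone give more power despite fewer patients, because those removed carry no information on the treatment effect.

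The gap depends on the assumed rates. Borrowing 62% vs 33% from the primary endpoint gives 71% vs 79% at q = 20% and 54% vs 68% at q = 40%. With 45% vs 20% it is 67% vs 71% and 51% vs 59%.

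**Damage index.** Six months is 365.25/2 = 182.6 days. Impairment starting on Day t can score from Day t + 182.6.

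- Read on Day 180: t must be no later than 180 − 182.6 = Day −2.6.
- Read at the end of the window, Day 183: t must be no later than about Day 0.4.
- Already scorable on Day 0: t no later than Day −182.6.

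An increase between the two readings therefore comes mainly from impairment that began in the half-year before Day 0. Because damage is defined as irreversible, the score should not fall either. This applies to every patient in the FAS.

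**The case against.** Much of the case on the other side stands. Section 8 leaves missing data, transformations and other data handling to the SAP, and Section 8.2.4 does the same for missing data in the secondary endpoints. A reader might infer that percent change for CLASI, joint counts and the damage index is a fatal error because a baseline of 0 is possible. The documents do not support that: Section 2.2 plans absolute change alongside percent change, the Protocol Summary plans ANCOVA adjusting for baseline where applicable, and a rule for zero baselines is ordinary SAP content. SLEDAI-2K has an entry floor in any case.

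A reader might also infer that CLASI response is counted in patients without skin disease. Section 6.3.5 limits it to patients with cutaneous activity, and Appendix 9 gives the reason: "Inclusion criteria could be met without presence of mucocutaneous disease". What remains is wording. "Response is defined as 50% improvement from baseline in" A or B scores does not say which CLASI score is meant; in Section 6.3.2 those letters are BILAG grades.

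On steroids, the companion endpoint is already restricted, and randomisation keeps the FAS comparison valid. The defect is dilution. On damage, an increase can still be scored for impairment that began before Day 0, and recent impairment that resolves on treatment would not be scored. A change of zero is therefore not guaranteed.

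None of this answers the two main points. The denominator and the reading days are fixed in the protocol itself, and the summary is explicit: "All efficacy analyses will be performed using the full analysis set (FAS").

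**Conclusion.** The point holds for two endpoints. The sustained steroid-reduction proportion includes certain non-responders. Its treatment difference shrinks by the share of patients on 0 mg at Day 0: from 20 points to 16-12 if that share is 20-40%, at a cost of about 4-5 points of power under true rates of 40% vs 20%. The share and the rates are assumptions, and higher success rates widen the loss. The damage index can hardly register damage arising on treatment; that conclusion needs only the persistence rule and the visit days.

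A reader might go further and call results on these endpoints uninterpretable. That does not follow. A positive steroid result on the FAS would still be a valid randomised finding, and a null one would be less informative than it could be. The damage index still describes the population. Percent change from zero and the CLASI wording are minor clarifications. The primary endpoint, alpha and sample size are untouched.

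**What to change.** 1. Analyse the sustained-reduction proportion in FAS patients receiving oral corticosteroid (more than 0 mg/day) at Day 0, and report how many that is per arm. This follows the principle already used for the companion endpoint, and the subset is defined before treatment. The cost is a smaller denominator. Restricting instead to patients above 7.5 mg/day would also remove steroid users who can succeed under the present definition, and could erase the gain: power is 0.389 if only 32:16 patients remain, at 40% vs 20%.

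2. Report the SLICC/ACR damage index descriptively and take it off the list of endpoints tested for superiority. This needs no new visit. Moving the second reading to Day 270 would change the schedule and still miss damage starting after about Day 87 (270 − 182.6 = 87.4).

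3. Minor: base the comparisons of CLASI and joint counts on the already planned baseline-adjusted absolute change, and use absolute change for the descriptive damage summary. State in Section 6.3.5 which CLASI score must improve by 50%.

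All of this is endpoint and SAP wording. It adds no patients and no assessments.
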